7.3. MISSING DATA

For the MMRM models, missing observations are treated as missing at random (MAR) and no imputation for missing data will be applied.

Unless otherwise specified, any individual missing item in any scale will not be imputed. When calculating a total score, subscale score, or any assessment with more than one item, if one or more items are missing at a visit, then the associated score (ie, total score or subscale score) will be set to missing. For additional details, see the individual scale description sections.

Handling of missing efficacy data, if any, is described in Sections [16.1.2](#), [16.2.2](#), [16.3.2](#).

Handling of missing safety data, if any, is described in Sections [17.1.1.1](#), [17.1.1.2](#), and [17.6](#).

Handling of missing PK data if any is described in [Section 18](#).

See [APPENDIX 2](#) for details of incomplete/missing dates.

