robustness of the conclusions, as indicated in [Section 16.2.4](#).

D. Population level summary of the variable: Difference in means of change from baseline in MADRS total score at Week 6 comparing each SEP-4199 treatment group to placebo

The efficacy of SEP-4199 in terms of the MADRS total score will be evaluated using the following two null hypotheses:

H1: There is no difference in mean change from baseline at Week 6 on the MADRS total score in the SEP-4199 200 mg treatment arm compared to Placebo.

H2: There is no difference in mean change from baseline at Week 6 on the MADRS total score in the SEP-4199 400 mg treatment arm compared to Placebo.

The alternative hypothesis for each of the null hypotheses is that there is a difference. If at least 1 of the primary treatment group comparisons demonstrate a significant result, the study will be considered positive.

The primary efficacy endpoint will be analyzed for the ITT population using an MMRM analysis, with change from baseline in the MADRS total score as the response variable and with factors for treatment group, week, region, baseline MADRS total score, and the treatment-by-week interaction. This analysis method makes an MAR assumption to the missing primary efficacy endpoints. The Kenward Roger approximation will be used to estimate denominator degrees of freedom. An unstructured covariance matrix will be used for the within-subject correlation. A robust sandwich estimator for the standard error of the fixed effects ([Diggle 2002](#)) along with a spatial exponential or a spatial power covariance structures will be assumed sequentially in case the model fails to convergence. The first covariance structure to yield convergence will be used in the analysis.

The Least Square (LS) mean treatment differences (each SEP-4199 group minus placebo) of change from baseline at Week 6, their 2-sided 95% CIs, and the associated p-values will be calculated based on the MMRM. The LS mean of change from baseline over time will be plotted. Adjusted p-values will be calculated using a truncated Hochberg procedure with gamma parameter=0.9 (See [Section 7.4](#)).

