At each postbaseline visit, within-group and between-group effect-size will be presented. Within-group effect size will be calculated as the absolute value of LS mean of change from baseline divided by SD, obtained as the SE of the LS Mean multiplied by the square root of the treatment group change from baseline sample size at each visit. Based on the MMRM, between-group effect size at a visit will be calculated as the absolute value of the LS means difference from placebo divided by the model estimate of the pooled SD at the visit, which is obtained from the square root of the diagonal element, associated at the visit, from the covariance matrix (R matrix of subjects with MADRS total score at all visits).

Multiplicity adjustment to control the global family wise Type I error rate at 5% is described in [Section 7.4](#).

The normality and homoscedasticity assumptions underlying the primary MMRM model will be assessed graphically and included in the SAS outputs. Shapiro-Wilk statistic will be included in the SAS output for exploratory purposes. Marginal studentized and Pearson residuals will be plotted against the predicted values, respectively, and quantile-quantile (Q-Q) plots of these residuals versus the expected quantiles of the standard normal distribution will be included in the SAS outputs to provide a graphical view of similarity and difference in the 2 distributions. Additional analyses may be explored to better understand the potential impact of any deviations on the interpretation of the primary efficacy analysis.

Document:

Author:

Version Number:

V2.0

Version Date:

21MAY2020

Template No: CS_TP_BS016 Revision 4
Effective Date: 01Apr2016

Reference: CS_WI_BS005

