APPENDIX 3. STATISTICAL MODEL SPECIFICATIONS

MIXED MODEL FOR REPEATED MEASURES (MMRM)

Ods graphics on;

```
PROC MIXED DATA=XXX plots=(studentpanel(marginal) pearsonpanel(marginal));
```

```
  CLASS SUBJID REGION TRTPN WEEK;  
  MODEL TOTCFB = TOTBL REGION TRTPN WEEK TRTPN*WEEK / DDFM=KR RESIDUAL OUTPM=OUTRESIDUAL;  
  REPEATED WEEK/TYPE=UN SUBJECT=SUBJID;  
  LSMEANS TRTPN*WEEK /PDIFF CL;
```

RUN;

*Where WEEK = Week 1, Week 2, Week 4, Week 6;

Ods graphics off;

In case the MMRM model assuming the unstructured covariance variance structure fails to converge, the spatial exponential or spatial power covariance structure will be assumed sequentially along with a robust sandwich estimator. The first covariance structure to yield convergence will be used in the analysis.

```
PROC MIXED EMPIRICAL;
```

```
  CLASS SUBJID REGION TRTPN WEEK;  
  MODEL TOTCFB = TOTBL REGION TRTPN WEEK TRTPN*WEEK / RESIDUAL OUTP=OUTRESIDUAL;  
  REPEATED WEEK/TYPE=SP(EXP) (WEEK) SUBJECT=SUBJID;  
  REPEATED WEEK/TYPE=SP(POW) (WEEK) SUBJECT=SUBJID;  
  LSMEANS TRTPN*WEEK /PDIFF CL COV;
```

RUN;

*EMPIRICAL IS FOR THE SANDWICH ESTIMATOR;

Within-group effect size will be calculated as the absolute value of LS mean of change from baseline divided by SD, obtained as the SE of the LS Mean multiplied by the square root of the treatment group change from baseline sample size at each visit. Between-group effect size at a visit will be calculated as the absolute value of the LS means difference from Placebo divided by the model estimate of the pooled SD at the visit, which is obtained from the square root of the diagonal element, associated at the visit, from the covariance matrix (R matrix of subjects with MADRS total score at all visits). Although the variance-covariance estimates are calculated differently depending on the covariance structure being applied for the model, the diagonal of the R matrix will contain the variance estimate at each visit that can be used for the effect size calculations regardless of the covariance structure.

Document:

Author:

Version Number:

V2.0

Version Date:

21MAY2020

Template No: CS_TP_BS016 Revision 4
Effective Date: 01Apr2016

Reference: CS_WI_BS005

For All SEP-4199 column for safety questionnaires:

- LS Means estimate, 95%CI and SE is obtained using following statements:

```
LSMESTIMATE TRT01PN*AVISITN "MEAN(200MG+400MG) at Week 1" [1, 1 1] [1, 2 1] / CL divisor=2;  

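### The within-group effect size divides by an MMRM standard error times √n, which is not the model SD once visit data are missing or the regions are unequal

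*SAP*

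**What the plan says.** SAP 16.1.3 plans two effect sizes at every post-baseline visit for the MADRS total score.

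- **Within group:** the absolute LS mean change divided by an SD, where the SD is "the SE of the LS Mean multiplied by the square root of the treatment group change from baseline sample size" at the visit. The MMRM part of Appendix 3 repeats this: "Within-group effect size will be calculated as the absolute value of LS mean of change from baseline divided by SD", with the same product as the SD.
- **Between groups:** the absolute LS mean difference "divided by the model estimate of the pooled SD at the visit, which is obtained from the square root of the diagonal element" of the residual covariance matrix R for that visit.

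The model behind both is the primary MMRM. "An unstructured covariance matrix will be used for the within-subject correlation". It is fitted jointly to four visits ("Where WEEK = Week 1, Week 2, Week 4, Week 6"), and SAP 7.3 states that "missing observations are treated as missing at random (MAR) and no imputation for missing data will be applied". The Appendix 3 code fits one covariance matrix for all arms and requests LS means without observed-margin weights, so US and Europe count equally whatever their size.

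SAP 16.1.5.1 uses the same within-group formula for the ANCOVA, which is fitted separately by week. Nothing elsewhere in the SAP corrects the MMRM version.

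**The concern.** Multiplying a standard error by √n recovers an SD when the standard error comes from a simple mean of n independent values. The Week 6 LS mean from this MMRM is not such a mean. A subject who stops after Week 2 still informs it through the Week 1 and Week 2 scores, but is not counted in the Week 6 sample size. The standard error therefore reflects more information than n represents, and the product is too small. In the by-week ANCOVA only observed cases enter, so there the formula is nearly right.

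The fitted model has one SD per visit. The formula nevertheless returns a different value for each arm, driven by how many subjects that arm lost and how the regions are split. The within-group figures would stand beside between-group figures scaled by the actual model SD, and an arm with more dropout would show a larger pre-post effect for the same LS mean change.

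**Working it through.** **Inputs from the documents.** 93 evaluable subjects per arm, difference -3.85 and SD 8.745 at Week 6 (SAP 3.4); visits at Weeks 1, 2, 4 and 6. The documents give no numerical within-group effect size to reproduce. The planning values are coherent: 3.85/8.745 = 0.44, and simulation of the truncated Hochberg test gives power 0.902 (at least one) and 0.746 (both), against 0.9027 and 0.7517 in SAP Table 8.

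**Inputs assumed, because the documents do not give them.** Dropout by Week 6 in US/Europe (15% or 30%, one third lost after each of Weeks 1, 2 and 4); visit-to-visit correlation 0.7 or 0.85, either the same for all pairs or decaying by visit (AR(1)); the US:Europe split; visit SDs 5, 6.5 and 8 before Week 6 (needed only for the region step and the spatial fallback). The only dropout figure in the documents is 9 of 45 (20%) for Japan.

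**Simplest case.** If a fraction d drops out just after the last earlier visit and R² is that of Week 6 on earlier visits, the formula returns SD × √(1 - R²d). With R² = 0.5:
- d = 10%: 8.745 × √0.95 = 8.52, effect size 2.6% too large
- d = 20%: 8.745 × √0.90 = 8.30, 5.4% too large
- d = 30%: 8.745 × √0.85 = 8.06, 8.5% too large

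**Dropout spread over visits, equal regions.** Let A, B and C be the R² of Week 6 on Week 1, on Weeks 1-2 and on Weeks 1-4, and let n1, n2, n4 and n6 be the fractions observed. With known covariance,

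(formula SD / true SD)² = A·n6/n1 + (B - A)·n6/n2 + (C - B)·n6/n4 + (1 - C).

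Example, common correlation 0.85 and 30% dropout (fractions 1, 0.9, 0.8, 0.7): 0.7225×0.7 + 0.0586×0.7/0.9 + 0.0217×0.7/0.8 + 0.1972 = 0.7675. The ratio is 0.876, and 1/0.876 = 1.14.

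| Correlation | A, B, C | 15% dropout | 30% dropout |
|---|---|---|---|
| AR(1) 0.70 | 0.118, 0.240, 0.490 | 0.978 (+2.3%) | 0.952 (+5.0%) |
| AR(1) 0.85 | 0.377, 0.522, 0.723 | 0.958 (+4.4%) | 0.911 (+9.8%) |
| Common 0.70 | 0.490, 0.576, 0.613 | 0.957 (+4.5%) | 0.911 (+9.8%) |
| Common 0.85 | 0.723, 0.781, 0.803 | 0.940 (+6.3%) | 0.876 (+14.1%) |

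Cells show the ratio and, in brackets, the error in the effect size. With no dropout the ratio is 1.00. A full generalised least squares calculation with treatment-by-week cells and region gives the same values.

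**Unequal dropout.** With 15% on placebo and 30% on active, dividing the two columns gives 0.978/0.952 = 1.03 up to 0.940/0.876 = 1.07. The active arms gain about 3-7% relative to placebo from the formula alone.

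**Early-termination mapping.** SAP 6.3, Table 1 assigns an early-termination MADRS on Days 31-44 to Week 6, and earlier ones to the next planned visit. If 80% of dropouts attend (assumed), 15% dropout gives fractions 1, 0.99, 0.94, 0.89. For common correlation 0.7 the ratio is then 0.967 rather than 0.957: 3.4% too large instead of 4.5%.

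**Unequal regions, no dropout.** With US fraction p and equal region weights, ratio² = 1 + [(0.5 - p)²/(3p(1 - p))] × v/8.745². Here v = 1/(1'Σ⁻¹1), where Σ is the assumed covariance matrix; v is 18.5 to 24.2 over the four patterns. At p = 0.25 the bracket is 0.0625/0.5625 = 0.111, so the ratio is 1.013 to 1.017 and the effect size is 1-2% too small. Adding 10% dropout at that split gives 0.97 to 1.00, so the two errors largely cancel.

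**The case against.** A reader might infer that within-group effect sizes are always overstated, or that the formula tilts the efficacy result towards the active arms. The documents support neither reading.

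- **Direction.** They give no dropout rate by arm and no US:Europe split. With unequal regions and little dropout the error can vanish or reverse. At a 20:80 split with 10% dropout it ran from 1.4% too small to 1.2% too large.
- **Unequal dropout.** The ordering (more dropout, more inflation) held in every unequal-dropout scenario tried, but it matters only if dropout differs by arm. The 15%/30% contrast is an illustration, not a forecast.
- **Size.** Early-termination mapping means that dropout is not the same as missing at Week 6, and it shrinks the error most for late dropouts. The Kenward-Roger adjustment, not modelled here, raises the SE slightly and also works against overstatement.
- **Importance.** The estimand and hypotheses H1 to H4 are between-group. No test compares within-group effect sizes across arms.
- **Choice of denominator.** The observed SD of change in each arm is also defensible, and using different denominators within and between groups is not in itself an error.

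All of this stands, and it limits the point to a conditional, modest error in a descriptive figure. It does not rescue the formula: the product is labelled an SD, and in this model it is one only without missing data and with balanced regions.

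**Conclusion.** The point holds in conditional form and is minor. The stated denominator is not the model SD when Week 6 data are missing or the regions are unequal. With equal regions, correlations of 0.7 to 0.85 and dropout spread over visits, the Week 6 within-group effect size is about 2-6% too large at 15% dropout and 5-14% too large at 30%, less after early-termination mapping. At a 25/75 split with no dropout it is about 1-2% too small. Dropout, correlation, region split and early-termination attendance are all assumptions. LS mean differences, their p-values, the multiplicity procedure, power and the between-group effect sizes do not use this quantity.

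**What to change.** In SAP 16.1.3 and Appendix 3, define the within-group effect size at a visit as the absolute LS mean change divided by the square root of the R-matrix diagonal element for that visit. This is the denominator already extracted for the between-group effect size.

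Add one condition. If the model falls back to the spatial exponential or spatial power structure, R has a single variance for all visits, although Appendix 3 treats its diagonal as usable under any structure. With visit SDs 5, 6.5, 8 and 8.745 that variance would be roughly (25 + 42.25 + 64 + 76.48)/4 = 51.9, an SD of 7.2. The Week 6 effect size would then be about 21% too large (8.745/7.2) and the Week 1 value about 31% too small (5/7.2). Under the fallback, use the observed SD of change at the visit instead.

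The cost is a line or two of wording and code. It needs no new data and changes no inference. The by-week ANCOVA formula in 16.1.5.1 can stay. Any within-group effect sizes produced for CGI-BP-S, HAM-A or QIDS-SR16 under the same MMRM method should follow the corrected definition.

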16.1.4. SENSITIVITY ANALYSIS OF PRIMARY EFFICACY VARIABLE

To address early dropouts under the assumption of missing not at random (MNAR), a pattern-mixture model (PMM) using a placebo-based multiple imputation method (O'Kelly 2014; Ratitch 2011) and a PMM using multiple imputations with penalties (ie, tipping point analysis by deflating the individually estimated treatment effect size by known factors) (Levin 2016; Permutt 2015; Ratitch 2013) will be performed as sensitivity analyses to explore the robustness of the MMRM results for the primary analysis based on the ITT population.

To address the impact of COVID-19, sensitivity analyses will be conducted to investigate the effect of visits conducted remotely, and the effect of COVID-19 overall as a general psychosocial stressor using the 11 March 2020 global pandemic declaration by the World Health Organization as a cutoff date.

Sites are instructed to enter the text "COVID-19 remote" on the comments CRF page for any clinic visits conducted remotely. If a visit is conducted remotely, any scale assessments collected during that visit will be assumed to be collected "remotely". In addition, if a video is used during the remote visit, the text "video" will be added to the above mentioned comment text. Remote scale assessments to be collected are MADRS, CGI-BP-S, YMRS, C-SSRS, PWC, HAM-A, SDS, AIMS, BARS, SAS, EQ-5D-5L, and QIDS-SR16. QIDS-16 is a self-reported paper base assessment which will be mailed to the subject. Each remote assessment will be flagged in its individual listing. Video assessments information will be available in the comments listing.

16.1.4.1. Dropout Profiles

Patterns of missing data in the primary endpoint will be assessed through graphical tools based on the reason and timing of study withdrawal by subjects.

Change from baseline in MADRS total score by week will be described and plotted by regrouped reasons of early discontinuation. Table 3 shows the regrouping of the reasons. Similar reasons may be combined according to the following table, depending on the number of subjects under each reason:

Table 3. Regrouping of reasons of early discontinuation.

CRF Term	Grouped Term
Adverse event	Adverse event
Death (due to AE)	Adverse event
Lack of efficacy	Lack of efficacy
Lost to follow-up	Lost to follow-up or Withdraw consent
Withdrawal by subject	Lost to follow-up or Withdraw consent
Pregnancy	Noncompliance and other
Noncompliance with study drug	Noncompliance and other
Protocol deviation	Noncompliance and other

Document:

Author:

Version Number:

V2.0

Version Date:

21MAY2020

Template No: CS_TP_BS016 Revision 4
Effective Date: 01Apr2016

Reference: CS_WI_BS005

Other reasons	Noncompliance and other
Termination by sponsor	Noncompliance and other

Change from baseline in MADRS total score by week will also be described and plotted based on the timing of termination for Visit 3/Week 1 terminators, Visit 4/Week 2 terminators, Visit 5/Week 4 terminators, Visit 6/Week 6 terminators, and completers, separately for each treatment group.

- o Visit 3/Week 1 terminators: subjects who discontinued after Visit 2/Baseline/Week 0 but before or on Visit 3/Week 1;
- o Visit 4/Week 2 terminators: subjects who discontinued after Visit 3/Week 1 but before or on Visit 4/Week 2;
- o Visit 5/Week 4 terminators: subjects who discontinued after Visit 4/Week 2 but before or on Visit 5/Week 4;
- o Visit 6/Week 6 terminators: subjects who discontinued after Visit 5/Week 4 but before or on Visit 6/Week 6;
- o Completers: subjects who completed the study treatment.

16.1.4.2. Pattern-mixture model with placebo-based multiple imputation

All ITT subjects are included in pattern-mixture model with placebo-based multiple imputation.

The MMRM model used in the primary analysis makes the assumption that data are MAR. However, the missing data mechanism may or may not be at random. Sensitivity to the missing data assumption will be tested by using the PMM with placebo-based multiple imputation method, exploring the robustness of the MMRM results of the primary efficacy analysis. In this analysis, missing values in the SEP-4199 (200 or 400 mg/day) treatment groups after remapping of the ET visits will be imputed based on data of the placebo group, assuming that after withdrawal, subjects from the SEP-4199 (200 or 400 mg/day) group will exhibit the same future evolution of depressive episode as subjects from the placebo group, and that subjects who discontinue from the placebo group will exhibit the same future evolution of depressive episode as subjects in the placebo group remaining in the study. This approach does not assume a sustained benefit of experimental treatment after discontinuation.

Two separate imputation procedures are used to impute missing values. Firstly, the Markov chain Monte Carlo (MCMC) method is used to perform partial imputation to obtain datasets with monotone missing patterns. Then a sequential regression multiple imputation method is used to impute the monotone missing values.

Under the assumption that the MADRS total scores have a multivariate normal distribution, the MCMC method is used to impute only intermittent missing values (using the SAS MI procedure with MCMC statement), by using a data augmentation algorithm, with each iteration n consisting of an imputation step and a posterior step. The imputation step uses a random draw of $\theta^{(n)}$, parameter of the joint imputation model, to sample missing values from a conditional distribution $P(Y_{mis}|x, y_{obs}, \theta^{(n)})$, obtaining $y_{mis}^{(n)}$, the subset of missing values that need to be filled in to achieve monotone missingness. The posterior step simulates a new draw of the parameter $\theta^{(n+1)}$ from the posterior distribution given the current monotone missing data $P(\theta|x, y_{obs}, y_{mis}^{(n)})$ with a non-informative Jeffreys prior. Treatment group will be taken into account for this imputation (ie, missing data at intermediate visits will be imputed for each treatment group using no-missing data from all subjects within the treatment group). These steps are repeated to obtain 1000 datasets with monotone missingness. The random seed number is 12345.

Document:

Author:

Version Number:

V2.0

Version Date:

21MAY2020

Template No: CS_TP_BS016 Revision 4
 Effective Date: 01Apr2016

Reference: CS_WI_BS005

The remaining monotone missing data will be imputed using sequential regression multiple imputation, where a separate regression model is estimated for imputation of each variable (ie, MADRS total score at each time point). Imputation of values in the placebo group will assume MAR. Imputation of values in the SEP-4199 (200 or 400 mg/day) group will be done as if the subject had been a member of the placebo group. Missing values in the SEP-4199 (200 or 400 mg/day) groups will be imputed using the imputation model of the placebo group, ie, conditional on subject values observed at time points prior to discontinuation. Each sequential regression model (ie, for imputation of values at a given time point) will include explanatory variables for all previous (Baseline, Week 1, Week 2, and Week 4) values of MADRS total score. Missing values at a given time point in placebo and SEP-4199 (200 or 400 mg/day) treatment groups will be imputed from the same imputation model, conditional on subject values observed or imputed at previous time points. The SAS MI procedure with the MONOTONE REG statement is used to specify that the regression method will be used for the imputation, and the MNAR statement with MODEL option will be used for the MADRS total score at each postbaseline visit to specify that only observations from the placebo group should be used to estimate the imputation model. The random seed number is 56789.

No rounding restriction will be applied to imputed MADRS total scores. The imputed MADRS total scores must be within the range of 0 to 60.

Each of the 1000 imputed datasets will be analyzed using the same MMRM model as the primary efficacy analysis. Results from the analysis of each imputed dataset, ie, the LS means of each treatment group, the LS mean treatment difference, and their standard errors, will be combined using Rubin's imputation rules (using the SAS MIANALYZE procedure) to produce pooled LS mean estimates, their standard errors and 95% CI, and a pooled p-value for the test of null hypothesis of no treatment effect.

